4.10.3 Imputation Rules for Incomplete Dates

In case of missing or partial start and stop dates for concomitant medications, the following rules will be used:

If the start date is missing or partial:

- if the month is missing, use January
- if the day is missing, use the first day of the month under consideration
- if the year is missing, use year of the informed consent date
- if the entire date is missing, use informed consent date

If the stop date is missing or partial:

- if the month is missing, use December
- if the day is missing, use the last day of the month under consideration
- if the year or the entire date is missing, set the stop date to December 31st, 2099

If the imputed start date is after the stop date, then the imputed start date will be 1 day prior to the stop date.

For AEs, a missing or incomplete onset date will be imputed according to the following conventions.

If an onset date is missing or only the year is known, the imputed onset date will be the date of first dose of study drug.

If only the year is known for the AE onset date, the imputed onset date will be the latest of the following non-missing dates:

- Date of first dose of study drug

- January 1 of the year of AE onset date

If only the month and year is known for the onset date, set the surrogate onset date to the first day of that month and then apply the following rules.

- If the month and year of the onset date is prior to the month and year of the first dose of study drug, then the surrogate onset date will be the imputed onset date.
- If the month and year of the onset date is on or after the month and year of the first dose of study drug, then the imputed onset date will be the **latest** of the following non-missing dates:
 - Date of first dose of study drug
 - Surrogate onset date
 - If the imputed onset date is after the adverse event end date, the imputed onset date will be the same as the adverse event end date.

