6.1.3 Start of Adverse Event Collection Period

If a subject experiences an AE after the informed consent document is signed, but before the Baseline/Control Baseline visit, the event will be considered medical history.

If a control subject experiences an AE after the Control Baseline visit but before the Baseline visit prior to dosing, the event will be considered a Control AE.

If the subject experiences an SAE after signing consent and before Baseline, it should only be reported as an SAE if the Investigator believes that the event may have been caused by a protocol-required procedure.

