7.4.1.1 Adverse Events

AEs will be coded using the Medical Dictionary for Regulatory Activities (MedDRA) dictionary.

Events will be identified as treatment-emergent (TEAE) and non-treatment-emergent (non-TEAE) on the basis of the date of onset relative to the date of AT132 dosing.

Number and percentage of subjects with TEAEs classified by system organ class (SOC) and preferred term (PT); by severity, causality, seriousness, and action taken with regard to study drug will be summarized. Number (%) of subjects with TEAEs leading to discontinuation of study will also be summarized. Hospitalization will be summarized by frequency (%) and duration. TEAEs and/or hospitalizations may be annualized.

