4.6.1 Adverse Events

Treatment-emergent AEs (TEAEs) are defined as any AEs, regardless of relationship to study drug, that have an onset or worsening in severity on or after the time/date of the baseline (dosing) visit (the reference date).

All descriptive statistics will be presented by dose level and all dose levels combined. Unless otherwise indicated, AE summaries will be presented by the following periods:

- Baseline through Week 24 (inclusive)
- >Week 24 through Week 48
- >Week 48 to End of Study
- Overall for the study

An overview table to report the number and percentage of participants and number of events will include the following:

- TEAEs,
- Drug related TEAEs,
- Serious TEAEs,
- Serious drug related TEAEs,
- TEAEs leading to withdrawal of study
- Drug-related TEAEs leading to withdrawal of study
- TEAEs leading to death,
- Drug related TEAEs leading to death,
- NCI-CTCAE Grade 3 or higher TEAEs
- NCI-CTCAE Grade 3 or higher drug related TEAEs
- Deaths

NCI-CTCAE v4.03 or higher will be used for assessment of grade.

The number and percentage of participants with TEAEs, as classified by SOC and PT will be summarized for each treatment group and overall. Summaries will be provided for the following:

- TEAEs
- Drug related TEAEs,
- Serious TEAEs,
- Drug related serious TEAEs,
- TEAEs leading to withdrawal of study,
- Drug related TEAEs leading to withdrawal of study,
- NCI-CTCAE Grade 3 or higher TEAEs,
- NCI-CTCAE Grade 3 or higher drug-related TEAEs,
- TEAEs leading to death,
- Drug-related TEAEs leading to death,
- Frequently reported ($\geq 10\%$ in All Dosed Group) TEAEs by preferred term,
- Frequently reported ($\geq 5\%$ in Any Treatment Group) TEAEs Excluding Serious TEAEs (this table will only be presented for the overall study duration)

Related AEs are those with relationship to study medication reported as “possible” or “related”. If relationship to study drug of an AE reported by treated participants is not recorded, the relationship will be imputed as “possibly related”, for analysis purposes. In the participant listing, both collected and imputed values will be presented.

An overview table to report number of events, and events adjusted by participant year from date of drug exposure (each summary classified by category below, SOC and PT) will include the following:

- Serious respiratory TEAEs,
- Serious non-respiratory TEAEs

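### SAP 4.10.3 gives two conflicting rules for an adverse event onset known only to the year, and neither keeps an earlier-year onset before dosing

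*SAP*

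**What the plan says.** SAP 4.10.3 deals with incomplete adverse event onset dates in three steps.

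- First rule: "If an onset date is missing or only the year is known, the imputed onset date will be the date of first dose". It covers a fully missing date and a year-only date alike.
- Second rule: "If only the year is known for the AE onset date, the imputed onset date will be the latest of the following non-missing dates". The candidates are the first-dose date and "January 1 of the year of AE onset date".
- Month-and-year rule: this one has a pre-dose branch. "If the month and year of the onset date is prior to the month and year of the first dose of study drug", the first day of that month is kept as the onset. Otherwise the later of that day and the first dose is used. A cap starting "If the imputed onset date is after the adverse event end date" is printed inside this rule's list and sets the onset to the end date.

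Treatment emergence rests on dates. SAP 4.6.1 counts events "that have an onset or worsening in severity on or after the time/date of the baseline (dosing) visit", and Protocol 7.4.1.1 classifies events "on the basis of the date of onset relative to the date of AT132 dosing". Unless otherwise indicated, SAP 4.6.1 splits adverse event summaries into Baseline to Week 24, after Week 24 to Week 48, after Week 48, and overall.

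For a control subject with an event between the Control Baseline visit and the Baseline visit before dosing, Protocol 6.1.3 says "the event will be considered a Control AE". The Study Design entry for version 3.0 in the SAP version history says that control-period data will not enter the analysis.

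**The concern.** A year-only onset meets both of the first two rules, and nothing says which prevails. If the first is programmed, an event from years after dosing is dated to Day 1 and appears as an acute post-dose event. Timing is part of the safety question here: Protocol 1.5 separates acute from chronic cardiac and creatine kinase findings and calls for long-term follow-up to understand them. The groups are small. Protocol 1.4.2 gives 6 and 17 dosed subjects at the July 2020 cutoff, so one child is 1/6 = 16.7% or 1/17 = 5.9% of a dose group in a by-period table.

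A second, separate gap is that both year-only rules floor at the first-dose date. An event from a calendar year before dosing would be placed on Day 1 if it reached these rules. Former controls are the subjects for whom this could happen, because Protocol 3.4 allows 24 weeks to 3 years of delay before dosing.

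**Working it through.** The plan gives no figure to reproduce, so the check applies the rules as written.

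**Inputs.** The rules are those of SAP 4.10.3. The period limits are Day 168 (Week 24) and Day 336 (Week 48), the scheduled days in Protocol 5.5; using them as the adverse event cut-offs is an assumption. Dose dates are illustrative. The dosing day is Day 1.

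**Formulas.** First rule: onset = dose date. Second rule: onset = max(dose date, 1 January of event year). If the dose falls on day *d* of a 365-day year, 1 January of the next year is study day 367 − *d*.

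**Worked example, dose on 1 March 2018 (*d* = 60).**

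| Event year | First rule | Second rule | Period under second rule |
|---|---|---|---|
| 2017 | Day 1 | Day 1 | Baseline to Week 24 |
| 2018 | Day 1 | Day 1 | Baseline to Week 24 |
| 2019 | Day 1 | 367 − 60 = Day 307 | Week 24 to 48 |
| 2021 | Day 1 | 307 + 365 + 366 = Day 1038 | After Week 48 |

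The first rule always gives Baseline to Week 24.

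**All 365 dose dates in a year.**

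- Event in the dosing year or the year before: the rules agree for 365 of 365.
- Event in the next year: the dates differ for 365 of 365. Under the second rule, Day 367 − *d* is at most 168 when *d* ≥ 199 (167 dates), 169 to 336 when *d* is 31 to 198 (168 dates), and above 336 when *d* ≤ 30 (30 dates). The reporting period therefore changes for 168 + 30 = 198 of 365.
- Event two years later: the second rule gives at least Day 367 − 365 + 365 = 367, so the period changes for 365 of 365. The same holds for any later year.

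**Earlier-year onsets.** In the 2017 row the true onset was before dosing. From 31 December 2017 to 1 March 2018 is 1 + 31 + 28 = 60 days, and from 1 January 2017 it is 60 + 364 = 424 days. Both rules still give Day 1. The month-and-year rule behaves differently: with dosing on 15 June 2019, an onset of November 2018 stays pre-dose, while the same event recorded only as 2018 goes to Day 1. If that event ended on 20 December 2018, the end-date cap would keep it pre-dose, but only if the cap covers year-only dates.

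**Whether such dates can arise.** A 24-week (168-day) control period reaches into the previous calendar year for 168/365 = 46% of dose dates. A period of one year or more does so for all of them.

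**The case against.** The strongest objection is to the pre-dose part. A reader might infer that control-period events will be counted as treatment-emergent. The documents do not support that. Protocol 6.1.3 defines Control AEs by visit, not by imputed date, and the SAP version history says control-period data will not be used. If those events are removed by study period, they never reach the date rules. For other subjects, events between consent and Baseline are medical history. This gap also does not come from the contradiction, since the two year-only rules agree for every year up to dosing. What stands is narrower: SAP 4.6.1 and 4.10.3 do not say that the separation comes before imputation.

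A reader might also think that no end-date cap exists. One does. It is printed among the candidates for a latest date, where it does not logically belong, so its limited reach may be only a formatting slip. Its scope needs stating.

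On impact, all summaries are descriptive, and year-only dates may be rare or absent. Events are elicited at each visit (Protocol 6.1.3.4), blank fields are not accepted unless allowed, and entries are source-verified and queried (8.6.1). Serious events are reported within 24 hours (6.2.2), and the admission date is the onset for hospitalizations (6.2.2.2). This limits the likely size, especially for serious events, but does not settle which rule applies. Visits after Month 60 are yearly and may be remote (5.2, 5.6), so imprecise onset dates remain plausible.

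**Conclusion.** The contradiction is certain from the text. For any event year after the dosing year the two rules give different dates, and the first reports a late event as a Day 1 event in the Baseline to Week 24 tables. Under the second rule the period differs for 198 of 365 dose dates when the event is in the next calendar year, and for all of them when it is two or more years later.

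It would be wrong to conclude that the contradiction inflates treatment-emergent totals: a late event is treatment-emergent under either rule, and only its date and period move. With 10-year follow-up the shift could approach 10 years, but that is a theoretical maximum. The number of year-only dates is not given, so the actual effect is unknown.

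The missing pre-dose branch is a real but conditional gap. It produces a false treatment-emergent event only if Control AEs are not set aside before imputation, and only for an incomplete onset date. In that case SAP 4.6.1 could add to the error, because it imputes an unrecorded relationship as possibly related. The correction is worth making before database lock, but does not threaten the analysis as a whole.

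**What to change.** Amend SAP 4.10.3 as follows.

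1. Remove the year-only case from the first rule, so that it covers only fully missing dates and the second rule governs year-only onsets.
2. Add a branch for an onset year before the dosing year that keeps the event pre-dose, parallel to the month-and-year rule (for example, 1 January of the recorded year).
3. State in 4.10.3, with a cross-reference in 4.6.1, that Control AEs are separated by study period before any date is imputed. The new branch does not make this unnecessary: a control event earlier in the dosing year, or one with a fully missing onset, would still be sent to the dosing date.
4. Move the end-date cap out of the month-and-year list and state that it applies to every imputed adverse event onset.

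The cost is a few lines of SAP text and the matching derivation code. No new data are needed.

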5 SUPPORTING DOCUMENTATION

5.1 Appendix 1 List of Abbreviations

Abbreviations	Description of abbreviations
ACEND	Assessment of Caregiver Experience with Neuromuscular Disease
AE	adverse event
AESI	adverse event of special interest
ALP	alkaline phosphatase
ALT	alanine transaminase
AST	aspartate transaminase
Bayley-III	Bayley Scales of Infant and Toddler Development III
BLD	below the limit of detection
CDI	Communicative Development Inventories
CGI-I	Clinical Global Impression of Improvement
CGI-S	Clinical Global Impression of Severity
CHOP INTEND	Children's Hospital of Philadelphia Infant Test of Neuromuscular Disorders
CI	confidence interval
CS	compound symmetry
DBP	diastolic blood pressure
DMC	data monitoring community
DMI	Developmental Milestone Identifiers
ECG	ectrocardiogram
ECHO	echocardiogram
FAS	full analysis set
GM	gross motor (Bayley)
GMFR	geometric mean fold rise
GMT	geomtric mean titer
ICH	International Conference on Harmonization
LAR	legally authorized representative
LLOQ	lower limit of quantification
LOCF	last observation carried forward
LS	least squares
MFM	Motor Function Measure scale
MIP	maximal inspiratory pressure
MMRM	mixed model repeated measures
n	participants
NCI-CTCAE	National Cancer Institute Common Terminology Criteria for Adverse Events
PCS	potentially clinically significant
PedsQL	Pediatric Quality of Life Inventory
PGIS-I	Parental Global Impression of Secretion Improvement
PGIS-S	Parental Global Impression of Secretion Severity
PT	preferred term
SAE	serious adverse event
SAF	safety analysis set
SAP	statistical analysis plan
SBP	systolic blood pressure
SD	standard deviation
SE	standard error
SMA-I	spinal muscular atrophy type I
SOC	system organ class
ULN	upper limit of normal
UN	unstructured
WHO	World Health Organization
XLMTM	X-Linked Myotubular Myopathy

5.2 Appendix 2 Unfavorable Values for Efficacy Estimand Imputation

Endpoint	Variable	Imputed value after ICE occurrence through Week 48
Primary	Hours of ventilation support	24 hours
Key Secondary	Achieving functionally independent sitting for at least 30 seconds	No (0)
Secondary	CHOP INTEND Total Score	0
	MIP	0
	Myotubularin expression	0
	ACEND total score	0
	PedsQL Scale	0
	PedsQL Summary Score	0
	Number of age-appropriate gross motor function milestones achieved	0
	Full ventilator independence achieved	No

ICE = intercurrent event

